7.6.2 Clinical Laboratory Evaluation

Laboratory parameters will be summarized by treatment group at each visit. Each summary will include the values of the laboratory parameters and their change from baseline. Shift tables from baseline will be presented for laboratory values in the chemistry and hematology panels that are captured categorically. Parameters will be classified as potentially clinically significant according to the criteria described in Appendix C. In addition, the laboratory results will be

graded by CTCAE v5.0 and the summary of treatment-emergent laboratory results by highest CTCAE grade will be summarized.

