#### 9.3 Planned Analyses

The analyses described in this section will be performed for data captured in Study Part 1 and Study Part 2 separately. No formal statistical inference is planned for data captured in Study Part 1.

As a general strategy, continuous efficacy and safety endpoints will be summarized using the five-number summary (mean, standard deviation, median, minimum, and maximum). Frequency distributions (counts and percentages) will be used to summarize categorical endpoints.

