#### 9.3.6.2 Clinical Laboratory Evaluation

Safety laboratory parameters will be summarized by treatment group at each visit. Each summary will include the values of the laboratory parameters and their change from baseline.

Shift tables from baseline will be presented for laboratory values in the hematology, chemistry, and coagulation tests. Parameters will be classified according to the laboratory reference normal ranges. A listing will be provided for out of normal range as well as potentially clinically significant abnormal laboratory values.

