# **APPENDIX 5** LABORATORY ASSESSMENTS

Hematology (Local Laboratory Tests)*	Serum Chemistry (Local Laboratory Tests)*		
Hemoglobin	Blood urea nitrogen (BUN)		
Hematocrit	Creatinine		
Total WBC count with 5-part differential	Sodium		
Platelet count	Potassium		
	Chloride		
	Carbon dioxide		
	Glucose		
Coagulation (Local Laboratory Tests)*	Total bilirubin		
Partial thromboplastin time (aPTT)	Direct Bilirubin		
Prothrombin time (PT)	Alkaline phosphatase (ALP)		
International normalized ratio (INR)	Aspartate aminotransferase (AST)		
	Alanine aminotransferase (ALT)		
	Additional Tests (Central Laboratory Tests)		
	D-dimer		
	Cardiac troponin		
	Ferritin		
	LDH		
	CRP		
	Exploratory tests (e.g., IL-6, TF, MCP-1, IP-10)		

\* Denotes laboratory assessment used primarily to generate safety summaries

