4.2 Efficacy Endpoints

The primary endpoints for Part 1 of the study are safety endpoints including treatment-emergent adverse events (TEAEs), vital signs and laboratory (hematology, chemistry, and coagulation) parameters and are described in Section 4.3. The secondary and exploratory efficacy endpoints for Part 1 are described in the following sections.

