4.3 Safety Endpoints

The following endpoints will be used to assess the safety and tolerability of ANA001:

- Incidence of treatment-emergent adverse events, serious adverse events, adverse events leading to study treatment discontinuation and adverse events leading to death
- Incidence of treatment-emergent potentially clinically significant laboratory abnormalities, including test results in the hematology, blood chemistry, and coagulation panels
- Incidence of vital signs abnormality, including temperature (°C), systolic and diastolic blood pressure (mmHg), pulse (beats/min), and respiratory rate (breaths/min).

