APPENDIX C. POTENTIALLY CLINICALLY SIGNIFICANT LABORATORY CRITERIA

| Local Laboratory | | | | | | | | | |
|----------------------------------|--------------------|----------------|-----------------|------------------------|------------------------|--|--|--|--|
| Parameter | SI Unit | Lower Limit | Higher Limit | % Decrease from BSL | % Increase from BSL | | | | |
| CHEMISTRY | | | | | | | | | |
| Blood urea nitrogen (BUN) | mmol/L | NA | >1.5*ULN | NA | >100 | | | | |
| Creatinine | mg/dL | NA | >1.5*ULN | NA | >50 | | | | |
| Sodium | mmol/L | <0.85*LLN | >1.1*ULN | >10 | >10 | | | | |
| Potassium | ∫mol/L | <0.8*LLN | >1.2*ULN | >20 | >20 | | | | |
| Chloride | mmol/L | <0.8*LLN | >1.2*ULN | >20 | >20 | | | | |
| Carbon dioxide (Bicarbonate) | | <0.7*LLN | >1.3*ULN | >40 | >40 | | | | |
| Glucose | mmol/L | <0.6*LLN | >3.0*ULN | >40 | >200 | | | | |
| Total bilirubin | mg/dL | NA | >2.5*ULN | NA | >150 | | | | |
| Direct bilirubin | mg/dL | NA | >1.5*ULN | NA | >150 | | | | |
| Alkaline Phosphatase | U/L | <0.5*LLN | >2.0*ULN | >80 | >100 | | | | |
| Aspartate Aminotransferase (AST) | U/L | NA | >3.0*ULN | NA | >200 | | | | |
| Alanine Aminotransferase (ALT) | U/L | NA | >3.0*ULN | NA | >200 | | | | |
| HEMATOLOGY | | | | | | | | | |
| Hematocrit | Ratio | <0.8*LLN | >1.3*ULN | >20 | >30 | | | | |
| Hemoglobin | g/L | <0.8*LLN | >1.3*ULN | >20 | >30 | | | | |
| Platelet Count | 10 ⁹ /L | <0.65*LLN | >1.5*ULN | >50 | >100 | | | | |
| White Blood Cell Count | 10 ⁹ /L | <0.65*LLN | >1.6*ULN | >60 | >100 | | | | |
| Neutrophils, absolute cell count | 10 ⁹ /L | <0.65*LLN | >1.6*ULN | >75 | >100 | | | | |
| Lymphocytes, absolute count | 10 ⁹ /L | <0.25*LLN | >1.5*ULN | >75 | >100 | | | | |
| Eosinophils, absolute count | 10 ⁹ /L | NA | >4.0*ULN | NA | >300 | | | | |
| Monocytes, absolute count | 10 ⁹ /L | NA | >4.0*ULN | NA | >300 | | | | |

| Basophils, absolute count | 10 ⁹ /L | NA | >4.0*ULN | NA | >300 | | | |
|--------------------------------------|--------------------|----------|----------|------|------|--|--|--|
| COAGULATION | | | | | | | | |
| Partial thromboplastin time (aPTT) | sec | <0.5*LLN | >2.0*ULN | >100 | >100 | | | |
| Prothrombin time (PT) | sec | <0.5*LLN | >2.0*ULN | >100 | >100 | | | |
| International normalized ratio (INR) | Ratio | <0.5*LLN | >2.0*ULN | >100 | >100 | | | |

LLN: Lower limit of normal value provided by the local laboratory ULN: Upper limit of normal value provided by the local laboratory BSL: Baseline

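### SAP 7.6.2 leaves coagulation out of the shift tables that the protocol calls for, and the Appendix C decrease criterion for aPTT, PT and INR can never be met

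*SAP*

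**What the plan says.** **Protocol.** Section 9.3.6.2 promises three panels: "Shift tables from baseline will be presented for laboratory values in the hematology, chemistry, and coagulation tests". It also names the categories: "Parameters will be classified according to the laboratory reference normal ranges". Section 9.3 applies this to both parts of the study: "The analyses described in this section will be performed for data captured in Study Part 1 and Study Part 2 separately". Appendix 5 lists the coagulation tests (aPTT, PT, INR) as local laboratory tests and marks that panel, with hematology and chemistry, by a footnote: "Denotes laboratory assessment used primarily to generate safety summaries".

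**SAP, shift tables.** Section 7.6.2 names two panels and adds a qualifier: "Shift tables from baseline will be presented for laboratory values in the chemistry and hematology panels that are captured categorically". It does not repeat the classification by reference range.

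**SAP, endpoints.** Section 4.2 lists among the Part 1 primary safety endpoints "vital signs and laboratory (hematology, chemistry, and coagulation) parameters". Section 4.3 adds: "Incidence of treatment-emergent potentially clinically significant laboratory abnormalities, including test results in the hematology, blood chemistry, and coagulation panels".

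**SAP, flag criteria.** The Appendix C columns are lower limit, higher limit, % decrease from baseline and % increase from baseline. The aPTT row reads "Partial thromboplastin time (aPTT) | sec | <0.5*LLN | >2.0*ULN | >100 | >100". PT and INR carry the same four entries. Neither Section 7.6.2 nor Appendix C says whether a flag needs the limit, the change, or both.

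**Version.** SAP Section 1 states that it was written to protocol Version 4.0 (Amendment 3). The protocol supplied is Version 5.0.

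**The concern.** There are two separate defects in how the SAP handles one panel.

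First, a programmer who follows SAP 7.6.2 produces no shift table for coagulation, although the protocol commits to one. The qualifier about categorical capture adds doubt for the two panels that remain. The listed tests are numeric by nature, and the text does not say how they become categories.

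Second, the low-side change criterion for all three coagulation tests is arithmetically impossible.

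What is at stake is descriptive but real. Coagulation belongs to the Part 1 primary safety endpoint. Protocol 2.1.2.5 and 2.1.2.6 describe COVID-19 as prothrombotic and suggest that ANA001 may lessen coagulation abnormalities, so movement in either direction is of interest. The tests are run at local laboratories across about 20 sites. A shift table judges each result against its own laboratory's range, which a by-visit mean does not do.

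**Working it through.** **1. Shift tables, side by side.**

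| | Protocol 9.3.6.2 | SAP 7.6.2 |
|---|---|---|
| Hematology | yes | yes, with qualifier |
| Chemistry | yes | yes, with qualifier |
| Coagulation | yes | not named |
| Categories | laboratory reference range | not stated |

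Coagulation tests with a planned shift table: 3 of 3 in the protocol, 0 of 3 in the SAP.

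**2. What the table would add to the flags.** The Appendix C limits for coagulation are wide. Take a participant whose baseline is at the ULN and whose value rises to 1.9 × ULN.
- Limit: 1.9 is not above 2.0, so it is not met.
- Change: 100 × (1.9 − 1.0)/1.0 = 90%, which is not above 100%, so it is not met.

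The participant is not flagged under either joining rule, but a shift table would show a move from normal to high.

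**3. The decrease criterion.**

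% decrease = 100 × (baseline − value)/baseline

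With baseline > 0 and value ≥ 0, the maximum is 100 × (baseline − 0)/baseline = 100%, reached only at a value of zero. A decrease above 100% cannot occur for aPTT, PT or INR.

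**4. Comparison with the rest of Appendix C.** Seventeen rows carry a decrease limit:
- sodium 10
- potassium, chloride, hematocrit and hemoglobin 20 each
- bicarbonate and glucose 40 each
- platelets 50
- white cells and LDH 60 each
- neutrophils and lymphocytes 75 each
- alkaline phosphatase and CRP 80 each
- aPTT, PT and INR 100 each

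Only the three coagulation rows are unattainable (17 − 3 = 14 others, from 10 to 80).

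**5. Consequence under each joining rule.**
- OR: the change criterion does nothing, and a low value is flagged only if it is below 0.5 × LLN.
- AND: both conditions are needed and one is impossible, so no low coagulation value can be flagged.
- Under both rules the high side (above 2.0 × ULN, rise above 100%) can be met.

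**6. How much the dead criterion costs under OR.** A working limit of T% flags values that the 0.5 × LLN limit misses only if baseline × (1 − T/100) > 0.5 × LLN. That means baseline > 0.5 × LLN/(1 − T/100). For scale only, T = 80 (the alkaline phosphatase value) gives 0.5/(1 − 0.8) = 2.5, so it would add flags only for baselines above 2.5 × LLN. If ULN = 1.5 × LLN (an assumption), that is 2.5/1.5 = 1.67 × ULN. A smaller T would act on more participants.

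**The case against.** The strongest reply is that the analysis of coagulation survives. SAP 7.6.2 still gives values and change from baseline by arm at each visit, classification against Appendix C, and the highest treatment-emergent CTCAE v5.0 grade. None of these excludes coagulation. Procoagulant harm is also approached through the blinded review of thromboembolic events (SAP 7.5.9) and the D-dimer criteria in Appendix C (above 1.0 × ULN, rise above 20%). If the drug lessens coagulation, prolonged clotting is the direction to watch, and that side of the criteria works. All of this stands. A reader might infer that a primary safety parameter goes without proper analysis, but the documents do not support that.

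Four other inferences also go too far.

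- *No shift table would be produced at all.* Appendix 5 lists test names and does not say how results are captured. Appendix C says the local laboratory supplies LLN and ULN, so low, normal and high classes are available. The qualifier may simply mean results classed in that way. It is unclear, but it does not prove that the tables would be empty.
- *Low coagulation values can never be flagged.* This holds only under AND, which the SAP does not state.
- *The limit should be 50%, as the two-fold mirror of a 100% rise.* Alkaline phosphatase has the same 0.5 × LLN, 2.0 × ULN and 100% rise, yet its decrease limit is 80. Two-fold symmetry is not an Appendix C convention.
- *The SAP departed from the protocol it was written to.* It cites Version 4.0, whose shift-table text cannot be checked here.

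It is also fair to say that the table shells are in a separate document, which may already include coagulation. That would not correct the SAP text.

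**Conclusion.** Both defects stand, in a limited form. Measured against protocol Version 5.0, the SAP omits the coagulation shift table (0 of 3 tests against 3 of 3). Appendix C also gives aPTT, PT and INR a decrease criterion that cannot operate. Those two things are what is lost; the other coagulation summaries remain.

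The effect of the dead criterion depends on a rule that the SAP leaves open. Under OR, flagging of low values rests on 0.5 × LLN alone. Under AND, there is no low-side flag.

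The 100% bound needs no assumption beyond a positive baseline and a non-negative value. The 1.67 × ULN illustration rests on the assumed ULN = 1.5 × LLN.

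Severity is minor. Part 1 safety is descriptive, in 60 participants (30 per arm), with no inferential test. Neither defect touches sample size, error rate or conduct.

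**What to change.** In SAP 7.6.2:
- Present shift tables from baseline in low, normal and high classes, by local laboratory reference range, for hematology, chemistry and coagulation.
- Delete the closing qualifier about categorical capture.

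In SAP Appendix C:
- Replace the decrease limit above 100% for aPTT, PT and INR with an attainable value below 100% that the sponsor justifies. The documents fix no value; alkaline phosphatase, whose other limits are the same, uses 80%.
- State for the whole table whether the limit and the change from baseline are joined by AND or OR.

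The SAP should also cite the protocol version that it implements, so that the two texts can be checked against each other.

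The cost is a few lines of text, three corrected cells and shift tables for three tests, all from data already collected.

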7.6.3 Vital Signs

Vital signs, including pulse, blood pressure, temperature, respiratory rate and body weight will be summarized by treatment group and time point. For each assessment of vital signs, change and percent change in vital signs from baseline will be summarized by treatment group.

8. VISIT WINDOW

Implementation of visit windows is not planned for the analysis of this study. Results will be analyzed according to reported visits.

9. MULTIPLICITY ADJUSTMENT

There are no plans to implement any adjustment to type-I error for Part 1 analyses as the primary endpoint is safety.

10. HANDLING OF MISSING DATA

10.1 Missing Efficacy Data

Missing data for the secondary efficacy endpoint is discussed in Section 7.4. Limited imputation of missing data is planned for exploratory efficacy endpoints.

10.2 Adverse Events Missing Data

Treatment-emergent adverse events (TEAEs) with missing severity will be considered Grade 3 and TEAEs with missing relationship will be counted as drug-related.

In cases where the start date is not complete, the assumption will be made that the adverse event is a treatment-emergent event unless there is evidence to the contrary. The first treatment start date will be used as the AE start date if the start date is missing. Missing adverse event end dates will not be imputed. The adverse event will be assumed to be ongoing if end date is missing.

10.3 Concomitant Medications Missing Dates

In cases where the start or stop dates are not complete, the assumption will be made that the medication is a concomitant medication unless there is evidence to the contrary.

If the year and month are available (and only day is missing) the first day of the month will be used to impute the start date, and the last day of the month will be used to impute the stop date.

If only the year is available and it is before the year of first study treatment date, January will be used to impute the start date and December will be used to impute the stop date. If the year is equal to the year of the first study treatment date, month and day of the first study treatment date

will be used to impute the start date, and month of the last study treatment date will be used to impute the stop date.

If the start or stop date is completely missing, the first study treatment date will be used to impute the start date, and the last study treatment date to impute the stop date.

Imputed dates will be used for categorization of medications to concomitant or prior, but data listings will present the date as recorded on the Case Report Forms.

SCHEDULE OF EVENTS (STUDY PART 1 AND STUDY PART 2) APPENDIX A.

| Study Day (All Study Days are calendar days) | Screening ^a | Day 1 | Day 2 ^b | Day 3 ^b | Day 4 | Day 5 ^b | Day 6 ^b | Day 7 ^b | Day 8/ET ^s | Day 15 | Day 28 | Day 60/ES ^b |
|--|------------------------|-------|--------------------|--------------------|-------|--------------------|--------------------|--------------------|-----------------------|---------|---------|------------------------|
| Window | 36 hours ^a | | | | | | | | | ±3 days | +2 days | +2 days |
| Informed consent | Х | | | | | | | | | | | |
| Demographics | Х | | | | | | | | | | | |
| Eligibility assessment | Х | | | | | | | | | | | |
| Medical history ^c | Х | | | | | | | | | | | |
| Height and weight for BMI ^d | | x | | | | | | | | | | |
| Randomization | | x | | | | | | | | | | |
| NEWS2 ^{e.n} , vital signs, COVID-19 severity and subjective symptoms of COVID-19 ⁿ | Х | Х | х | × | х | Х | х | × | Х | Х | х | Х |
| Record SpO ₂ and supplemental oxygen, and type of ventilation, if applicable ^{e,f} | Х | Х | Х | Х | Х | X | х | Х | Х | Х | Х | Х |
| Complete physical examination (excluding GU) | | Х | | | | | | | Х | | | |
| Targeted physical examination | Х | | | | | | | | | | | |
| Study drug administration ^g | | Х | Х | Х | Х | Х | Х | Х | Х | | | |
| Serum chemistry ^{h, p} | | Х | Х | Х | Х | Х | Х | Х | Х | | | |
| Hematology and coagulation ^{i, p} | | Х | Х | Х | Х | Х | Х | Х | Х | | | |
| D-dimers (central lab) ^j | | Х | | | Х | | | | Х | | | |
| CRP (central lab) ^j | | Х | | | Х | | | | Х | | | |
| Cardiac troponin (central lab) ^j | | Х | | | Х | | | | Х | | | |
| LDH (central lab) ^j | | Х | | | Х | | | | Х | | | |
| Ferritin (central lab) ^j | | Х | | | Х | | | | Х | | | |
| NP swab for confirmation of SARS-CoV-2 with RT-PCR ^k (local site lab) | Х | | | | | | Per lo | Per local SOC | | | | |

21

| Window | 36 hours ^a | | | | | | | | | ±3 days | ±3 days +2 days | +2 days |
|---|-----------------------|-----------|------------|-----------|------------|----------|---------------|------------|-------------|--------------|-------------------|---------------|
| NP swab for confirmation of SARS-CoV-2 with qRT-PCR ^k (central lab) | | Х | | | Х | | | | Х | Х | X | |
| PK sampling ¹ (Part 1 Only) | | | | X | | | | | | | | |
| WHO Ordinal Scale for Clinical Improvement ^{e,m} | Х | Х | Х | Х | Х | X | X | X | Х | X | Х | Х |
| Chest X-ray | | | | | | Per | Per local SOC | 7) | | | | |
| AE assessment ^e | Х | Х | x | х | Х | х | x | x | Х | Х | X | X |
| Concomitant medications ^{e,r} | Х | Х | Х | Х | Х | Х | Х | Х | Х | Х | Х | Х |
| SOFA¢,0 | | Х | Х | Х | Х | Х | Х | Х | Х | Х | Х | Х |
| Blood for exploratory tests ^j (e.g., IL-6, Tissue Factor, MCP-1 and IP-10) | | Х | | | | | | | Х | | | |
| Serum pregnancy test for females of childbearing potential | Х | | | | | | | | | | | |
| ^a Screening assessment are to be completed within 36 hours of randomization. Screening and Day 1 may occur on the same day if results are available to confirm | completed wi | thin 36 l | nours of r | andomizat | ion. Scree | ning and | Day 1 ma | y occur or | the same da | y if results | are availab | le to confirm |

participant eligibility (SARS-CoV-2-positive NP swab confirmed with RT-PCR or alternative Sponsor approved assay at screening).

- It may not be possible to conduct all study visits in-person due to quarantine and other infection control measures. In case where in-person visits are not possible, telemedicine appointments should be conducted. All visits are required to be conducted as in-person visits (due to sample collection requirements) except for Days 2, 3, 5, 6, and 7 (if discharged home with study drug for self-administration) and the EOS/Day 60 (+2) visit which may be conducted by a telemedicine appointment. For telemedicine appointments, all data should be collected, and the following should be reviewed/discussed in detail with the participant: AEs, clinical status, and hospital readmission. م
 - and respiratory distress. Other medical history within 14 days prior to enrollment and presence of comorbidities especially cardiovascular disease, pulmonary disease Any history or current presence of signs and symptoms associated with COVID-19 within 14 days prior to screening, including fever, cough (productive or nonproductive), sore throat, malaise, headache, muscle pain, gastrointestinal symptoms (i.e., nausea, vomiting, or diarrhea), shortness of breath (with or without exertion), (e.g., COPD, asthma), hypertension, diabetes, and obesity, is to be recorded.
 - If the participant is unable to be measured for weight and height, stated weight and height is acceptable. σ
- Assessments should be collected daily while hospitalized including any day after Day 8 that the patient remains in the hospital. NEWS2 (Appendix 2) score to be If mechanically ventilated (or ECMO), document PaO₂ and FiO₂. SpO₂ and any supplemental oxygen saturation and rate at SpO₂ determination timepoint; also, any assessed 2 to 6 hours post-first dose per day. If first dose assessments are missed, use the same collection timepoint post-second dose of the day (2-6 hours post-dose). noninvasive ventilation (No, yes; if yes, designate type). For intubated patients, record PaO₂ and FiO₂ values of the worst P-F ratio of the calendar day. e

- NG or OG tube. Please refer to the Pharmacy Manual for instructions for NG or OG administration. Total duration of study drug administration is a 7-day course of (defined as 14 doses administered BID). ANA001 or matching placebo should be taken with a meal. If the participant is ventilated, study drug may be administered via Dosing should be performed within 36 hours of screening and continue until the treatment course is completed. Study drug is to be administered for 7 consecutive days treatment. 50
- Chemistry labs to be collected pre-dose (prior to first study drug dose of the day) and include the following: BUN, creatinine, sodium, potassium, chloride, carbon dioxide, glucose, direct bilirubin, total bilirubin, ALP, AST, and ALT ч
 - Hematology and coagulation samples will be collected prior to first study drug dose of the day and include a CBC (consisting of hemoglobin, hematocrit, total WBC count with 5-part differential, and platelet count) plus a partial thromboplastin time (aPTT), a thrombin time (PT), and an international normalized ratio (INR).
- Test sample is for central lab assessment. Additionally, a central lab blood sample for each participant and timepoint collected will be stored for possible virology testing (e.g., genotypic resistance testing).
- Sponsor approved assay used by the investigational site is to be obtained at Screening prior to baseline (Day 1). If a positive RT-PCR result for SARS-CoV-2 was NP swab for assessment of viral load is to be obtained at the indicated timepoints. Laboratory-confirmed SARS-CoV-2 infection as determined by RT-PCR, or other collected as part of SOC during the study screening window, the result may be used to fulfill the applicable inclusion criteria. Quantitative assessment of viral load by qRT-PCR will be performed by an external central lab. Please refer Central Laboratory Manual for sample collection instructions. NP swab may be collected at any time during the day.
